8.3 Prior Hypotheses

The purpose of this study is to perform analyses that will inform us on the long-term safety of ivacaftor use in patients with CF. Given the known safety profile of ivacaftor, this study will further characterise the safety of chronic ivacaftor treatment in real-life use and provide descriptive analyses on specified safety and CF disease progression outcomes using observational data. These analyses will be used for hypothesis generation for safety issues that warrant future study. Therefore, no prior hypotheses are proposed for the primary objectives. Prior hypothesis is provided for specific secondary objectives, although the study may be underpowered to detect any differences:

- Pulmonary exacerbations: similar or lower incidence in the Ivacaftor Cohort than the Comparator Cohort and previously observed in the pivotal Phase 3 studies (as described in the Summary of Product Characteristics [SmPC])
- Adverse drug reactions (as listed in the SmPC): similar or lower incidence in the Ivacaftor Cohort than the Comparator Cohort and previously observed in the pivotal Phase 3 studies (as described in the SmPC)
- Serious adverse events and adverse events leading to withdrawal of ivacaftor: similar or lower incidence in the Ivacaftor Cohort than the Comparator Cohort (CF Trust data only).

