9.1.1 Study Population

The Ivacaftor Cohort will include all patients who have been treated with ivacaftor and are enrolled in the CF Trust or CF Foundation patient registries. The Comparator Cohort will include patients who have never been exposed to ivacaftor and are matched on age group, *CFTR* genotype class, and sex (see Section 9.2.4) to patients in the Ivacaftor Cohort.

The Ivacaftor Pregnancy Study Cohort will include all female patients who have ivacaftor exposure in the analysis year and are enrolled in the CF Trust or CF Foundation patient registries. The Comparator Pregnancy Study Cohort will include female patients who have never been exposed to ivacaftor and are matched on *CFTR* genotype class to patients in the Ivacaftor Pregnancy Study Cohort (see Section 9.2.4).

The Comparator and Comparator Pregnancy Study Cohorts will be identified for each registry's Ivacaftor and Ivacaftor Pregnancy Study Cohorts, respectively, at a ratio of m:1, where m is the maximum number of matches available.

The Historical Cohort will include patients who have the *G551D-CFTR* mutation, were enrolled in the patient registries before ivacaftor was available in clinical studies and commercially in the US and the UK (i.e., 2008), and were never exposed to ivacaftor.

The Drug Utilisation Cohort will include all patients who have ever been treated with ivacaftor.

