9.1.2.2 Comparator Cohort

Inclusion Criteria

1. Patients with CF in the CF Trust or the CF Foundation patient registries

2. Patients with no evidence of ivacaftor exposure (current or past)
3. Patients matched to patients in the Ivacaftor Cohort on age group, *CFTR* genotype class, and sex (see Section 9.2.4 for matching criteria)

Exclusion Criterion

1. Participation in an interventional study during the analysis period (if available)

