9.3.1 Variables for Cystic Fibrosis Trust Patient Registry (UK)

9.3.1.1 Exposure

Ivacaftor exposure will be determined by first evidence of ivacaftor treatment and patients will remain exposed until there is evidence of discontinuation of ivacaftor in the patient registry database. Because start and stop dates are available, ivacaftor exposure will be calculated in days. When start and stop dates are not available due to missing data, algorithms will be used to extrapolate duration of exposure based on timing of patient encounters and drug exposure data available. The exposure algorithm includes the following rules: if only month and year are available, then the assumed start or stop date will be the 15th of the month, or if only year is available, then the assumed start or stop date will be June 30th. Ivacaftor exposure will be categorised into the meaningful groups based on the distribution of exposure, such as <1 year, 1 to <2 years, and ≥2 years. For patients who discontinue treatment with ivacaftor, reason for discontinuation (lack of benefit, side effect, other) will be described.

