9.3.1.2 Outcomes

Death will be defined if there is evidence of a date of death in the database. Cause of death will include respiratory/cardiorespiratory, liver disease, trauma, suicide, transplant-related, and other.

Organ transplantations will be defined if there is evidence of an organ transplantation. Type of transplant will include lung and other.

Hospitalisations will be defined if there is evidence of a start date for a hospitalisation for a pulmonary exacerbation.

CF complications include the following:

- allergic bronchial pulmonary aspergillosis (ABPA)
- absence of vas deferens
- arthritis
- arthropathy
- asthma
- bone fracture
- cancer confirmed by histology
- cardiac disease
- CFRD
- chronic *P aeruginosa* colonisation
- chronic *Staphylococcus aureus* colonisation
- cirrhosis with portal hypertension
- cirrhosis with no portal hypertension
- depression
- DIOS
- fibrosing colonopathy/colonic stricture
- gallbladder disease requiring surgery
- gastroesophageal reflux disease (GERD)
- gastrointestinal (GI) bleed (non-variceal) requiring hospitalisation
- GI bleed (variceal) requiring hospitalisation
- Haemoptysis
- Hearing loss
- hypertension
- kidney stones
- liver disease, non-cirrhosis
- liver enzymes elevated
- nasal polyps requiring surgery
- nontuberculous mycobacteria (NTM) infection (not requiring treatment)
- NTM infection (requiring treatment)
- osteopenia
- osteoporosis
- pancreatitis
- peptic ulcer disease
- pneumothorax requiring chest tube
- port inserted or replaced
- rectal prolapse
- renal failure requiring dialysis
- septicaemia
- sinus disease
- other, specify including cataract

Pulmonary exacerbations will be defined by evidence of a CF care episode or hospitalisation with reason pulmonary exacerbation. Respiratory microbiology will include patients with a bacterial culture and evidence of chronic colonisation with *Staphylococcus aureus*, chronic *P aeruginosa*, intermittent *P aeruginosa*, *Burkholderia*, methicillin-resistant *Staphylococcus aureus*, and *Haemophilus influenzae*.

Serious safety outcomes will be defined by combining death, organ transplantations, hospitalisations, and selected CF complications.

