Given the scientific interest in the assessments of pulmonary exacerbations and adverse events in the CF population, a null hypothesis would be that there is no difference in the incidence of these events between Ivacaftor and Comparator Cohorts or perhaps a lower incidence in the Ivacaftor Cohort. However, the analyses are limited by a number of factors. The lack of knowledge on the background risk of specific adverse events in the target CF population means that it is not possible to predict whether the number of patients in each registry will be sufficient to power the detection of statistically significant differences between the Ivacaftor and Comparator Cohorts. The small sample size may also lead to spurious results that may confound interpretation, and the manner in which pulmonary exacerbations are collected do not allow direct comparison to the incidence of pulmonary exacerbation observed in Phase 3.

For the specific prior hypothesis on pulmonary exacerbation, the CF Trust and CF Foundation registries do not predefine the clinical presentations that constitute a pulmonary exacerbation. Therefore, there is likely some variability in pulmonary exacerbation events within each registry and across both registries. Further, because the data sets are based on existing registry variables, adverse drug reactions, and adverse events in the SmPC will rely on mapping variables and/or rely on CF care centres providing text entries that are mappable.

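### The prior hypothesis on adverse events leading to withdrawal of ivacaftor is set against a never-exposed cohort, whose incidence is zero by definition, so the comparison is uninformative

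*Protocol*

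**What the plan says.** Section 8.3 proposes no hypotheses for the primary objectives but gives three for secondary objectives, with a caveat that power may be low. The abstract repeats them.

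- The third, restricted to CF Trust data, covers serious adverse events and "adverse events leading to withdrawal of ivacaftor: similar or lower incidence in the Ivacaftor Cohort than the Comparator Cohort".
- Section 9.1.1 fixes the comparison group: "The Comparator Cohort will include patients who have never been exposed to ivacaftor". Section 9.1.2.2 makes this an inclusion criterion, "Patients with no evidence of ivacaftor exposure (current or past" being the operative words, and Section 9.2.3 says the same.
- The only UK source for a withdrawal event is the exposure record in Section 9.3.1.1: "For patients who discontinue treatment with ivacaftor, reason for discontinuation (lack of benefit, side effect, other) will be described". Table 4 lists a stop reason for the UK registry only, which fits the restriction to CF Trust data.
- The first hypothesis, on pulmonary exacerbations, and the second, on adverse drug reactions, also compare with incidence in the pivotal Phase 3 studies. The third does not.
- Section 9.9, on the limits of these hypotheses, says that the ways in which exacerbations are collected "do not allow direct comparison to the incidence of pulmonary exacerbation observed in Phase 3".

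**The concern.** A between-cohort comparison of incidence needs an event that can occur in both cohorts. Withdrawal from ivacaftor can occur only in a patient who has taken it. The third hypothesis therefore joins a valid contrast (serious adverse events) to one in which one side is fixed by the cohort definition.

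The stake is interpretation. These three bullets are the only prior hypotheses in a post-authorisation safety study, and Section 12 says its results will be used to adjust the Risk Management Plan. A reported difference in withdrawal events would look like evidence about excess risk, although nothing was learned from the comparators. A finding of no difference would look like reassurance, although it would reflect only a small count on ivacaftor.

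No section repairs this. The caveat in Section 8.3 concerns power. Section 9.9 covers background risk, sample size, event definition and mapping of terms, but not an outcome that comparators cannot have.

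**Working it through.** **The definitions together.** Let p_I be the incidence of adverse events leading to withdrawal of ivacaftor in the Ivacaftor Cohort and p_C that in the Comparator Cohort.

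1. Sections 9.1.1, 9.1.2.2 and 9.2.3: every comparator patient is never exposed. Section 9.3.1.1: stop reasons exist only for patients who stop ivacaftor. Hence p_C = 0 exactly, whatever the sample size.
2. Risk difference: p_I − p_C = p_I, which cannot be negative. A lower incidence on ivacaftor cannot occur.
3. Relative risk: p_I / 0, undefined.
4. Equality holds only if no ivacaftor patient has the event.

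**What a test would show.** The protocol assigns no test and no margin to the word *similar*. As an illustration only, take the convention of Table 6, the protocol's one power calculation (death rates): one-sided Fisher exact test, alpha 0.1, equal groups. Exact enumeration under that convention reproduces the table: at relative risk 2, power is 0.386 against a stated 0.393 for N = 432, and 0.706 against 0.703 for N = 1035; at relative risk 3 and N = 432, 0.769 against 0.772.

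Inputs: 432 exposed UK patients (the best case in Section 9.5 and Table 6); m comparators per exposed patient, which Section 9.1.1 leaves open, so m = 1, 2 and 4 are assumed here. For x events against 0:

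p(x) = C(432, x) / C(432(m + 1), x)

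For example, x = 2 and m = 1: (432 × 431) / (864 × 863) = 186,192 / 745,632 = 0.250.

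| x | m = 1 | m = 2 | m = 4 |
|---|---|---|---|
| 1 | 0.500 | 0.333 | 0.200 |
| 2 | 0.250 | 0.111 | 0.040 |
| 3 | 0.125 | 0.037 | 0.008 |
| 4 | 0.062 | 0.012 | 0.002 |

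At alpha 0.1 the largest non-significant count is 3 of 432 (0.7%) at 1:1, 2 at 2:1 and 1 at 4:1. The result thus depends on the ivacaftor count and on how many comparators were matched, although extra comparators add no information about an event they cannot have.

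**How often events would appear.** The documents give no withdrawal rate. For assumed true risks q, P(at least 1 event) = 1 − (1 − q)^432:

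| Assumed q | P(at least 1) | P(at least 4) |
|---|---|---|
| 0.1% | 0.35 | 0.001 |
| 0.5% | 0.89 | 0.17 |
| 1% | 0.99 | 0.63 |
| 2% | 1.00 | 0.97 |

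Across this range the comparison would pass or fail according to p_I alone.

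**Phase 3 wording.** The exacerbation bullet in Section 8.3 sets incidence against Phase 3; Section 9.9 says exacerbations as collected cannot be compared directly with Phase 3. These two passages conflict. For the second bullet, which reads "Adverse drug reactions (as listed in the SmPC): similar or lower incidence in the Ivacaftor Cohort than the Comparator Cohort and previously observed" in Phase 3, Section 9.9 states only that terms will have to be mapped. The conflict is therefore limited to exacerbations.

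**The case against.** The strongest reply is that little hangs on this. Section 8.3 calls the analyses descriptive and hypothesis-generating, Section 9.3.4 allows risk differences as well as relative risks, and Section 9.3.1.1 already promises a description of stop reasons, so much of the right report is planned. That limits the consequence, but it does not give the comparison a meaning.

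A reader might also infer four stronger points, which the documents do not support:

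- *The hypothesis can only fail.* No margin is set for *similar*. Zero events satisfies it, and up to 3 events in 432 at 1:1 would not be significant at alpha 0.1.
- *Any trivial count becomes a significant excess.* At 1:1, 4 events are needed at alpha 0.1. Higher ratios lower that number, but m is not fixed, 432 is a best case, and the Fisher test appears only in the note to Table 6.
- *Section 9.9 gives up the Phase 3 comparison altogether.* It does so for exacerbations only, and the bullet on withdrawal contains no such comparison. Section 9.9 is also open about the limitation, so what remains is a wording conflict.
- *The UK serious-event comparison hides a non-respiratory harm.* UK hospitalisations are indeed narrow: "Hospitalisations will be defined if there is evidence of a start date for a hospitalisation for a pulmonary exacerbation". However, Section 9.3.4.1 analyses death with its cause, transplantation and CF complications separately, and the UK complication list includes gastrointestinal bleeds requiring hospitalisation, septicaemia and renal failure requiring dialysis. The protocol also never equates serious adverse events with its composite of serious safety outcomes.

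**Conclusion.** The point stands in a narrow form. The withdrawal half of the third prior hypothesis has a comparator incidence of exactly zero by definition, so the contrast is uninformative and can never favour ivacaftor. This follows from the cohort and exposure definitions and needs no numerical assumption. The Fisher and binomial figures only illustrate it; they rest on 432 exposed patients, assumed matching ratios and assumed event risks.

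The size is modest: half of one secondary, descriptive hypothesis is wrong as written, in Section 8.3 and in the abstract. The serious adverse event half has a valid comparator. Study size, Table 6 and the primary objectives are unaffected. It is worth correcting because a statistical analysis plan that carried out the hypothesis as fixed would inherit the empty comparison. The Phase 3 conflict in the exacerbation bullet is real but secondary.

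**What to change.** In Section 8.3 and in the abstract:

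1. Remove adverse events leading to withdrawal of ivacaftor from the between-cohort hypothesis. Report them for the UK Ivacaftor Cohort alone, as an incidence with an exact 95% confidence interval, using the stop reason *side effect* from Section 9.3.1.1. This stays informative when counts are small: with 0 events in 432, the two-sided upper limit would be 1 − 0.025^(1/432) = 0.0085, or 0.85%.
2. Keep the between-cohort hypothesis for serious adverse events.
3. Delete the Phase 3 comparison from the exacerbation bullet, or reconcile it with Section 9.9.

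The cost is edits to two bullet lists and one table from data the registry already collects. Half of one hypothesis is withdrawn. No additional composite endpoint is needed.

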9 RESEARCH METHODS

9.1 Study Design

To evaluate the long-term safety and CF disease progression in patients with CF who are treated with ivacaftor, this PASS comprises observational cohorts of patients receiving ivacaftor who are in the CF Trust and the CF Foundation patient registries. Existing CF registries provide an established source to obtain long-term safety in a real-life setting for analysis. The CF Trust and CF Foundation patient registries provide the ideal source to obtain long-term safety information because the data collected are extensive and consistent with one another. In addition, the patients with CF from the CF Trust and the CF Foundation patient registries encompass a majority of the patients in the indicated population. The encounter-based patient data collected by the registries constitute secondary data; no primary data will be collected for this study. Each registry will conduct an annual analysis of data accumulated in the previous year.

Given the global prevalence of CF, the limited size of the CF population indicated for treatment with ivacaftor (i.e., *G551D* mutation), and the availability of national registries of patients with CF that currently collect data on treatment patterns, safety, and pulmonary function outcomes of patients with CF, Vertex decided to work with the patient registries in the UK and in the US to meet the study objectives. This decision was made based on feedback from CF healthcare providers who indicated that a separate ivacaftor registry would be burdensome to patients and staff at CF care centres. In addition, the patients followed in these registries are expected to be representative of patients with CF with the *G551D* mutation globally. However, additional sources of patient data from the EU are under investigation for inclusion into the drug utilisation objective (Study Objective 3 [Section 8.1]).

Observational or noninterventional study design is the preferred method used to understand the safety of products in the "real-world" setting and allows for data collection of outcomes without influencing treatment patterns. Once market authorisation is achieved, it is expected that a broader patient population will be exposed to the drug compared to the population exposed in the clinical development programme. The observational design allows for the study of outcomes in the newly exposed population and, because of the availability of historical data for patients enrolled in the registries, previously exposed patients. With this design, we estimate that a subset of patients who were exposed to ivacaftor during clinical development and continue to be treated with ivacaftor will have exposure durations of greater than 5 years when analysed for the annual reports.

9.1.1 Study Population

The Ivacaftor Cohort will include all patients who have been treated with ivacaftor and are enrolled in the CF Trust or CF Foundation patient registries. The Comparator Cohort will include patients who have never been exposed to ivacaftor and are matched on age group, *CFTR* genotype class, and sex (see Section 9.2.4) to patients in the Ivacaftor Cohort.

The Ivacaftor Pregnancy Study Cohort will include all female patients who have ivacaftor exposure in the analysis year and are enrolled in the CF Trust or CF Foundation patient registries. The Comparator Pregnancy Study Cohort will include female patients who have never been exposed to ivacaftor and are matched on *CFTR* genotype class to patients in the Ivacaftor Pregnancy Study Cohort (see Section 9.2.4).

The Comparator and Comparator Pregnancy Study Cohorts will be identified for each registry's Ivacaftor and Ivacaftor Pregnancy Study Cohorts, respectively, at a ratio of m:1, where m is the maximum number of matches available.

The Historical Cohort will include patients who have the *G551D-CFTR* mutation, were enrolled in the patient registries before ivacaftor was available in clinical studies and commercially in the US and the UK (i.e., 2008), and were never exposed to ivacaftor.

The Drug Utilisation Cohort will include all patients who have ever been treated with ivacaftor.

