 - Congenital anomalies
3. Drug utilisation
 - Ivacaftor exposure in patients with CF
4. CF disease progression
 - CF lung disease severity based on percent predicted FEV₁
 - Clinical signs of CF disease progression
 - Change in lung function over time

Data Sources

1. CF Trust Patient Registry (UK)
2. CF Foundation Patient Registry (US)

In both registries, all patients participate in standard encounter-based data collection including annual assessments for death, organ transplantation, hospitalisations, complications, pulmonary exacerbations, respiratory microbiology, pregnancy, and pulmonary function. Investigators at CF care centres enter data for their enrolled patients with CF into the registry databases. In both registries, investigators are physicians at certified CF care centres. Data collection forms were developed to capture pertinent data related to CF and the medical care of patients with CF. Changes to data collection forms have been incorporated over the years using a process where changes requested by investigators are reviewed and approved by the governing committee for each registry. The data elements collected are provided in standard terms for diagnoses and treatments and are considered adjudicated diagnoses.

Additional data sources (European CF Society Patient Registry and national registries in Ireland, France, and Germany) were evaluated (see Annex 3). Based on the completed feasibility assessment, these data sources are appropriate for the drug utilisation analysis (Objective 3).

Study Size Ivacaftor is indicated for the treatment of CF in patients 6 years of age and older who have a *G551D* mutation in the *CFTR* gene. The estimated prevalence of the *G551D* mutation is approximately 2374 patients globally. Based on 2010 data, the CF Trust has enrolled 432 patients with the *G551D* mutation¹ and the CF Foundation has enrolled 1035 patients with the *G551D* mutation.² A Comparator Cohort will be identified for each registry's Ivacaftor Cohort at a ratio of m:1, where m is the maximum number of matches available. The Historical Cohort will comprise patients with the *G551D* mutation who do not have evidence of treatment with ivacaftor through clinical studies.

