9.1.2.3 Historical Cohort

Inclusion Criteria

1. Patients with CF in the CF Trust or the CF Foundation patient registries
2. Patients with the *G551D-CFTR* mutation
3. Patients with no evidence of ivacaftor exposure before ivacaftor was available commercially

Exclusion Criterion

1. Participation in an interventional study during the analysis period (if available)

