9.2.3 Study Cohorts

Patients from the patient registries will be categorised into 6 cohorts.

1. The Ivacaftor Cohort will include all ivacaftor-treated patients enrolled in the CF Trust or CF Foundation patient registries, regardless of age, *CFTR* genotype, or pulmonary function.

2. The Comparator Cohort will include patients who are not receiving and have never received ivacaftor and are a match on age group, *CFTR* genotype class, and sex to patients in the Ivacaftor Cohort. Based on the mechanism of action of ivacaftor and the availability of genetic testing, it is expected that most patients with *G551D-CFTR* mutation will be exposed to ivacaftor during the study period, making it challenging to identify a comparator cohort of patients with CF with the *G551D-CFTR* mutation who are not exposed to ivacaftor. Therefore, patients in the Comparator Cohort will be matched on *CFTR* genotype class based on the functional classification of *CFTR* alleles.^{14,22}
3. The Historical Cohort will include patients who have the *G551D-CFTR* mutation, were enrolled in the patient registries in 2008 (before ivacaftor was available in clinical studies and commercially in the UK and the US), and have no evidence of exposure to ivacaftor.
4. The Ivacaftor Pregnancy Study Cohort will include all female patients 13 years of age or older who were enrolled in the patient registries and were treated with ivacaftor.
5. The Comparator Pregnancy Study Cohort will include female patients who are not receiving and have never received ivacaftor and are a match on *CFTR* genotype class to patients in the Ivacaftor Pregnancy Cohort.
6. The Drug Utilisation Cohort will include all patients who were enrolled in the patient registries with evidence of ivacaftor exposure.

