9.2.5 Other Matching Considerations

Given the limited size of the CF population, the Comparator and Comparator Pregnancy Cohorts will not be matched for other measures of disease severity (e.g., percent predicted FEV₁, *Pseudomonas aeruginosa* infection) due to concerns about availability of adequate patients for matching. However, measures of disease severity will be included as stratification variables and as covariates for adjustment, as necessary.

The Historical Cohort will include patients with a *G551D-CFTR* mutation who were in the patient registries in 2008. These patients were chosen because they represent the best match to ivacaftor-treated patients in 2012 and later because they match the indicated patient population based on the approved product labelling. The Historical Cohort will include patients of all ages and will be stratified to identify outcomes for patients younger than 6 years of age (for the potential off-label population). The year 2008 was chosen because starting in 2009, ivacaftor clinical studies were actively enrolling in the UK and US. A 1-year window was selected to match the window for safety outcome analysis in the Ivacaftor and Comparator Cohorts. The Historical Cohort will be analysed once for Objectives 1 and 2 for all stratification variables. If additional analyses are identified during the conduct of the study, the Historical Cohort will be available for analysis.

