The use of a Historical Cohort may also introduce bias in several ways. Data from a Historical Cohort are, by definition, different from the Comparator Cohort (selected from the same period as the Ivacaftor Cohort) because the CF care (e.g., medications, nonpharmacologic therapies, and treatment guidelines) have changed over time. Additionally, because the majority of patients with the *G551D* mutation are likely to be currently receiving ivacaftor, the Historical Cohort is likely to comprise the same patients, but at a different disease state (e.g., higher lung function, fewer clinical signs, and symptoms). The data fields for the registries are also modified slightly over time, limiting the ability to directly compare data from the Historical Cohort with those of cohorts based on more recent time periods.

Limitations on power and sample size

The number of patients included in annual analyses will be dependent on the use of ivacaftor amongst patients in the registries. As of 2010, the enrollment of patients with the *G551D-CFTR* mutation is 432 in the CF Trust and 1035 in the CF Foundation.^{1,2} Therefore, the power to detect differences in the study endpoints is limited. Whilst we explored the study power for detecting differences in mortality, the study is powered to detect 2- to 3-fold differences between study cohorts. One method to increase power would be to combine data from individual patient registries. Combining data sources was previously considered by the leadership of the patient registries in the UK and US independent of this study protocol, and they advised that previous pooled analysis has been limited to matching at the encounter level and methods for combining annual data have not been established. Throughout the conduct of the study, the feasibility of combining annual registry data will be further explored.

Limitations on the analyses for prior hypotheses

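### The protocol gives conflicting exposure rules for the 2008 Historical Cohort, and any rule that removes patients does so on events after 2008, which inflates the historical death rate

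*Protocol*

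**What the plan says.** The exposure rule for the Historical Cohort differs from place to place in the protocol:

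- **Section 9.1.1**: G551D patients enrolled before ivacaftor was available, "i.e., 2008), and were never exposed to ivacaftor". There is no time limit on exposure.
- **Section 9.2.3**, repeated in the Abstract under Study Design: G551D patients enrolled in 2008 who "have no evidence of exposure to ivacaftor". Again there is no time limit.
- **Section 9.1.2.3**, repeated in the Abstract under Study Population: "Patients with no evidence of ivacaftor exposure before ivacaftor was available commercially". Patients first treated after launch stay in.
- **Abstract, Study Size**: G551D patients "who do not have evidence of treatment with ivacaftor through clinical studies".
- **Section 9.2.5**: G551D patients of all ages who were in the registries in 2008, with no exposure condition.
- **Section 9.9**: because most G551D patients are probably now treated, "the Historical Cohort is likely to comprise the same patients, but at a different disease state".

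Section 9.2.5 also gives the reason for the year, "The year 2008 was chosen because starting in 2009, ivacaftor clinical studies were actively enrolling in the UK and US", and for the window, "A 1-year window was selected to match the window for safety outcome analysis in the Ivacaftor and Comparator Cohorts". The cohort is drawn with the Year 1 Report in 2013 (Tables 1 and 2, footnotes). Table 5 makes its results available for comparison with the ivacaftor-treated cohorts under Objectives 1 and 2, judged by 95% confidence intervals.

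**The concern.** The rules cannot all describe one cohort. Each registry runs its own analysis (Section 9.3.4), so the two could build different cohorts under the same name. The launch cut-off in Section 9.1.2.3 also falls on different dates: Section 6 gives February 2012 for the US and January 2013 for the UK.

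The second problem is selection on the future. Nobody in the UK or US registries could have been exposed in 2008, so a filter applied as of 2008 removes no one. A filter that does remove someone must use information from 2009 or later. A patient who died in 2008 could never be treated afterwards and always stays in. A survivor who later took ivacaftor leaves the denominator.

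Concurrent comparators are matched to F508del (Section 9.2.4), so the Historical Cohort is the only reference group defined by G551D. In a safety study, an inflated reference death rate errs in the unwelcome direction: it makes ivacaftor look protective or hides an excess.

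**Working it through.** **Inputs**

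- Annual death proportion without ivacaftor: 103/9385 = 0.01097, stated as 0.011 (Section 9.5).
- G551D patients: 432 in the UK and 1035 in the US (Section 9.5). These are 2010 counts, used here as a stand-in for 2008.
- u, the share of 2008 survivors later exposed and so removed. The protocol gives no figure at the 2013 extraction. Values of 10%, 25% and 50% are assumed.

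**The plan's own figures.** Table 6 is the only death-rate calculation in the protocol, and none is given for the Historical Cohort. Exact power for a one-sided Fisher test at alpha 0.1 with equal groups reproduces it. At relative risk 2 it gives 0.386 (stated 0.393) for 432 per group and 0.706 (stated 0.703) for 1035. Table 6 is sound and is not affected by this point.

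**Is a filter needed?** Outcome year: 2008. First UK and US trial enrolment: 2009. Exposure possible in the outcome year: none. The filter therefore protects against nothing in the 2008 data.

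**Effect on the death rate under the never-exposed rule.** With d the true 2008 death proportion, all deaths are kept and a fraction 1 − u of survivors is kept:

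rate after selection = d / [d + (1 − d)(1 − u)]

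- u = 0: 0.01097, or 4.7 deaths of 432 and 11.4 of 1035.
- u = 0.10: 0.01097 / (0.01097 + 0.98903 × 0.90) = 0.0122, which is 1.11-fold.
- u = 0.25: 0.01097 / (0.01097 + 0.98903 × 0.75) = 0.0146, which is 1.33-fold.
- u = 0.50: 0.01097 / (0.01097 + 0.98903 × 0.50) = 0.0217, which is 1.98-fold.

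The multiplier does not depend on cohort size. For the US count, the 11.4 deaths would sit in a cohort cut from 1035 to about 933, 779 or 523 patients.

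**Effect on the comparison.** The apparent relative risk of ivacaftor against the Historical Cohort is the true value divided by the multiplier, with other differences between the periods set aside:

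| Survivors removed | True RR 1 appears as | True RR 2 appears as |
|---|---|---|
| 10% | 0.90 | 1.80 |
| 25% | 0.75 | 1.51 |
| 50% | 0.51 | 1.01 |

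**The narrower rules.** Sections 9.1.2.3 and the Abstract's study-size text also act on events after 2008, namely trial participation from 2009. They remove fewer survivors, so the same formula applies with a smaller u. The protocol gives no count of trial participants, so no figure can be put on it.

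**The case against.** The best defence is that the never-exposed wording is loose drafting. The formal inclusion criterion keeps patients first treated commercially, Section 9.2.5 has no filter, and Section 9.9 expects the same people in both cohorts. The Section 9.2.3 wording might even mean exposure as of 2008, which would remove nobody. This may be the intent, but it does not clear the text. Section 9.1.1 rules out any exposure, and a window running to launch or a reference to clinical studies necessarily reaches past 2008.

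A reader might infer a far larger bias, since Section 9.2.3 expects that most patients with the G551D "mutation will be exposed to ivacaftor during the study period". The formula gives about 4.8-fold at 80% removed and 9.1-fold at 90%. The documents do not support these values at the extraction: the statement covers the whole study period, while the cohort is drawn in 2013 from data up to the previous calendar year and analysed once for Objectives 1 and 2. UK ivacaftor use was not collected until 2013 (Table 2, footnote b), so few or no UK patients could be removed then. In the US, marketed use would show only from February 2012.

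A reader might also infer that every historical event rate is inflated. The arithmetic shows this only for death. For transplants, hospitalisations, exacerbations, complications and pregnancy, survivors treated later may have been sicker or healthier in 2008 than those never treated, and the protocol does not settle which.

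It also stands that the cohort is a descriptive reference. The planned relative risks and risk differences are against the concurrent Comparator Cohort. Section 9.9 already warns of bias from changes in care, disease state and data fields, but not of this selection.

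**Conclusion.** Wrong as written. The conflict between the definitions can be seen in the text and needs no assumption. The upward bias in the historical death rate follows whenever the rule removes a survivor, because no 2008 death can be removed for later exposure. Its size depends on the share removed, which the documents do not give; the 1.11- to 1.98-fold range rests on the assumed 10% to 50%. At Year 1 the effect would be mainly in the US, and it is smaller under the launch and clinical-study wordings. Section 9.2.5 keeps the cohort available for further analyses, so a later re-extraction under the never-exposed wording would enlarge the bias as uptake grows. For non-fatal outcomes and pregnancy the cohort is still selected on the future, but the direction is unknown.

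**What to change.** Use one definition throughout: all patients with a G551D allele and a registry record in calendar year 2008, with exposure status fixed at 2008 and no filter on later ivacaftor use.

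The exposure wording has to be changed in at least six places: the Abstract (Study Design, Study Population and Study Size) and Sections 9.1.1, 9.1.2.3 and 9.2.3. It should then agree with Section 9.2.5 and with the overlap expected in Section 9.9. The cost is a text edit before the Year 1 extraction. The extract becomes simpler and no smaller, and no new data are needed.

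Allowing for patients who appear in both cohorts when an interval compares historical with treated patients is optional and can be left to the SAP.
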